Subjects eligible for inclusion in the treatment holiday group will **not** be recruited from the long-term continuation studies LBSL99 or HGS1006-C1066, due to regulatory commitments for completing 10 years and 5 years on treatment, respectively. However, subjects who discontinue belimumab treatment in studies LBSL99 or HGS1006-C1066 can be recruited into the long-term discontinuation group in the present study.

For subjects entering the study, a minimum of 6 months previous participation in an open-label continuation study will provide subjects initially randomized to placebo in parent studies with the opportunity to reach sufficient biological activity to achieve a belimumab pharmacological and/or clinical response.

CONFIDENTIAL

The target sample size of at least 10 subjects in the treatment holiday group and at least 26 subjects in the control group is based on estimates of subject eligibility and number of subjects from continuation study BEL114333 anticipated to provide consent to participate in this study. The target sample size of 35 subjects for the long-term discontinuation group is based on practical considerations of numbers of subjects anticipated to drop-out and not on statistical considerations.

Enrolment of subjects from the 3 belimumab continuation studies into the long-term discontinuation group will remain open while recruitment to the treatment holiday and control groups is ongoing or until 36 months have elapsed since study start. A target sample size of 35 subjects in the long-term discontinuation group is anticipated.

Because this study is non-randomized, subjects and investigators from study BEL114333 will jointly decide upon which of the three groups to enrol into. Subjects recruited from the HGS1006-C1066 and the LBSL99 studies may only choose to enter the long-term discontinuation group, as they elect to no longer receive further belimumab therapy.

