6.1.2. Secondary Endpoints

The secondary endpoints are:

- Rate of any SLE Flare Index flares.
- Time to first severe SLE Flare Index flare.
- Number of subjects in the treatment holiday and long-term discontinuation group with evidence of rebound (defined as a SELENA SLEDAI score during the first 24 weeks that exceeds the baseline SELENA SLEDAI score in the original parent study.
- Number of subjects with confirmed true positive belimumab anti-drug antibodies (ADA) by the end of the study.
- Percentage change from baseline in:
 - Total serum immunoglobulin (IgG, and other isotypes: IgM and IgA)
 - Autoantibodies (anti-dsDNA, ANA), and complement (C3, C4)
- Percent change in absolute B cell subsets (CD20+, CD20+/27+ memory, CD20+/27naïve, CD20+/69+ activated, CD20+/138+ plasmacytoid, CD19+/27BRIGHT/38BRIGHT SLE subset and CD20-/138+ plasma cells) at Weeks 0, 8, 16, 24, 32, 40 and 52 and from Weeks 24 to 52.
- Absolute change in SELENA SLEDAI score.
- Number of days of daily prednisone dose ≥7.5 mg/day and/or increased by 25% from Day 0 of this study to Week 24, from Day 0 of this study to Week 52, and from Week 24 to Week 52.
- Number of days of daily prednisone dose ≤7.5 mg/day and/or decreased by 25% from Day 0 of this study to Week 24, from Day 0 of this study to Week 52, and from Week 24 to Week 52.

Note: baseline is the time before any treatment with belimumab, which was Day 0 of the original parent studies that fed into the 3 continuation studies from which subjects were recruited into this study. When Day 0 is used in relation to endpoints, this refers to Day 0 of this study.

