Supplementary study conduct information not mandated to be present in this protocol is provided in the accompanying Study Procedures Manual (SPM). The SPM will provide the site personnel with administrative and detailed technical information that does not impact subject safety.

Amendment 01, Section 3.2 Discussion of Design

This study proposes to recruit subjects from 3 ongoing open-label continuation studies of belimumab in SLE subjects as well as from the open-label period of BEL113750 for China subjects in order to obtain an eligible population in the shortest timeframe:

- BEL114333: A Phase III open-label continuation of parent study BEL113750, which is an ongoing Phase III, double-blind, placebo-controlled study of belimumab in SLE subjects conducted in Japan and South Korea.
- BEL113750: Only China subjects from the open-label portion of this Phase III, randomized, parallel group, double-blind study to evaluate the efficacy and safety of 10mg/kg belimumab intravenously at Weeks 0, 2, and 4, and then every 4 weeks, compared with placebo over a 52-week treatment period in subjects with active systemic lupus erythematosus (SELENA SLEDAI score ≥ 8) in Northeast Asia.
- HGS1006-C1066: An ongoing Phase III, open-label continuation study of parent study HGS1006-C1056 (BLISS 76), which enrolled and treated 268 SLE subjects with belimumab conducted in the United States
- LBSL99: An ongoing Phase II, open-label continuation study of parent study LBSL02, which enrolled and treated 296 SLE subjects with belimumab conducted in the United States and Canada.

Subjects eligible for inclusion in the treatment holiday group will have been treated with belimumab for at least 6 months in BEL114333 or for at least 6 months in the BEL113750 open-label period for China subjects, and have a SELENA SLEDAI score \leq 3 and complement (C3 and C4) levels at or above the central laboratory lower limit of normal.

Subjects eligible for inclusion in the control group will have been treated with belimumab for at least 6 months in BEL114333 or for at least 6 months in the BEL113750 open-label period for China subjects, and have a SELENA SLEDAI score ≤ 3 and complement (C3 and C4) levels at or above the central laboratory lower limit of normal but elect to continue their current treatment with belimumab 10 mg/kg.

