5.3. Baseline Definitions

5.3.1. Baseline Definitions¹

The baseline (BL) definition is dependent upon the endpoint being analyzed.

• For the SELENA SLEDAI (including rebound), immunoglobulins, autoantibodies, complement, BLyS and B-cell endpoints, baseline is defined as the Day 0 assessment in the subject's respective parent study, prior to exposure with study treatment (whether placebo or belimumab). Baseline data for these

parameters will be extracted from the ADaM data sets from the double blind study (LBSL02, BEL110751, BEL113750 or BEL112341) from which the patients are enrolled.

- For the SLE flares, SLE severe flares, SLICC, prednisone (7 day average prior to Day 0), PGA, and immunogenicity², endpoints, baseline is the Day 0 assessment in BEL116027.
- For other endpoints, baseline is the Day 0 assessment in BEL116027².

¹Feeder study BEL114333 database had not yet completed at the time of BEL116027 Last Patient Last Visit. Consequently, baseline data for BEL114333 patients has not been fully cleaned when extracted from that study's database for reporting.

²Assessments covered for both Day 0 in BEL116027 and the Exit/Follow-up visit of the feeder continuation studies were only to be performed once and were to be recorded in the appropriate case report forms for each study. For Day 0 values not recorded in BEL116027 CRF but exist in the feeder study, the data will be extracted from the appropriate feeder study for inclusion in analysis

In the displays, the baseline value/visit will be denoted as Baseline.

See Section 13.4.1 for a diagram depicting the baseline definitions and phases.

Definition	Reporting Details
Change from Baseline	= Post-Dose Visit Value – Baseline
% Change from Baseline	= 100 x [(Post-Dose Visit Value – Baseline) / Baseline]
Maximum Change from Baseline	= Calculate the change from baseline at each given timepoint
	and determine the maximum change

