7.2.1.3. Rebound

Rebound is defined as a SELENA SLEDAI score during the first 24 weeks that exceeds the baseline SELENA SLEDAI score in the subject's respective original parent study.

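### For subjects randomised to placebo in the parent study, rebound is judged against the score before placebo rather than the score from which belimumab was started, so their rebound status can be misread

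*SAP*

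**What the plan says.** Protocol Section 6.1.2 makes rebound a secondary endpoint for the treatment holiday and long-term discontinuation groups. Its note says "baseline is the time before any treatment with belimumab, which was Day 0 of the original parent studies".

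SAP Section 7.2.1.3 keeps that definition: rebound is "a SELENA SLEDAI score during the first 24 weeks that exceeds the baseline SELENA SLEDAI score in the subject's respective original parent study". SAP Section 5.3.1 fixes the baseline at parent Day 0, "prior to exposure with study treatment (whether placebo or belimumab"), with the values taken "from the double blind study (LBSL02, BEL110751, BEL113750 or BEL112341").

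Protocol Section 3.2 explains the six-month minimum in an open-label study by saying it will "provide subjects initially randomized to placebo in parent studies with the opportunity to reach sufficient biological activity", so parent-placebo subjects are expected. Protocol Appendix 7 describes BEL113750 as testing belimumab "compared with placebo over a 52-week treatment period" in subjects with a SELENA SLEDAI score of at least 8.

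Rebound is reported in Table 2.6, which SAP Section 13.11.5 marks as a headline result. The only planned split (SAP Section 7.2.3) is by the score at Day 0 of this study, 3 or below against above 3.

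**The concern.** A subject randomised to belimumab started the drug at parent Day 0, so the benchmark is also the level at which treatment began. A subject randomised to placebo started belimumab only after the blinded period. Parent Day 0 is still before any belimumab, as the protocol note says, but a stretch of placebo plus standard of care lies between it and the first dose.

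If activity fell over that stretch, a subject can rise above the pre-belimumab level after stopping and still not exceed parent Day 0, and so is not counted. If activity rose, a return to the pre-belimumab level, or to a point short of it, can be counted as rebound. Table 2.6 mixes both kinds of subject without showing which is which.

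Rebound is a stated purpose of the study and part of a post-marketing commitment to the EMA. The groups are small, so a few reclassified subjects move the reported percentages visibly. The same baseline feeds the SELENA SLEDAI change and the biomarker changes. For parent-placebo subjects those changes therefore include the placebo period.

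**Working it through.** The plan states no rebound rate, power or threshold to reproduce, so the check is of the definition, followed by an illustration of size.

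**Definition.** Let D be the parent Day 0 score, P the last score before the first belimumab dose, and X a score in the first 24 weeks of this study. The SAP counts X > D. A pre-belimumab benchmark counts X > P. The two rules differ only when
- P < X ≤ D: above the pre-belimumab level, not counted;
- D < X ≤ P: counted, not above the pre-belimumab level.

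Examples with assumed scores:
- D = 10, P = 6: scores 7 to 10 are not counted.
- D = 8, P = 12: scores 9 to 12 are counted.
- D = P: no difference.

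If the BEL113750 entry threshold also held at Day 0, D ≥ 8 and rebound needs X ≥ 9.

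**Length of the gap.** For BEL113750 it is 52 × 7 = 364 days. Protocol Section 8 tabulates placebo flare rates over 52 weeks for the pooled BLISS studies but does not give the full placebo duration of BLISS 76. No duration is given for LBSL02 or BEL112341.

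**Number affected.** SAP Section 2.3 gives 12 holiday and 39 long-term discontinuation subjects enrolled, 12 + 39 = 51. The parent-placebo share is not given. At assumed shares:

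| Share | Of 51 | Of 12 | Of 39 |
|---|---|---|---|
| 0 | 0 | 0 | 0 |
| 20% | 10.2 | 2.4 | 7.8 |
| 33% | 17 | 4 | 13 |
| 50% | 25.5 | 6 | 19.5 |

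One reclassified subject moves the holiday percentage by 1/12 = 8.3 points and the long-term discontinuation percentage by 1/39 = 2.6 points.

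**Illustration, parent-placebo subjects only, all inputs assumed.** D is normal with mean 10 and SD 2.5, rounded, with a minimum of 8. The fall D − P has SD 3. The peak X has mean 4 or 6 and SD 4. P and X are rounded with a minimum of 0. There are 400,000 draws per setting. Shares are of all parent-placebo subjects; the ranges span the two peak means.

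| Mean fall on placebo | Above P, not counted | Counted, not above P |
|---|---|---|
| 0 | 6-8% | 2-4% |
| 2 | 13-18% | 1-2% |
| 4 | 24-31% | under 0.5% |
| 6 | 37-44% | 0.1% |

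At a one-third share and a mean fall of 4, this is 4 × 0.24 to 0.31, about 1 holiday subject, and 13 × 0.24 to 0.31, about 3 to 4 long-term discontinuation subjects. Undercounting grows with the fall on placebo, but the documents do not report that fall.

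**The case against.** The strongest reply is that rebound is defined against the original parent-study baseline in both documents, and the SAP names the placebo case openly. Whether stopping leaves a subject worse than at entry to the programme is a coherent question. That stands. A reader might infer that the SAP departs from the protocol or contains an error; it does neither.

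Changing the main analysis would also bring its own trouble. Selection at a score of 8 or more acts on Day 0 in both parent arms. Moving only placebo subjects to a later, unselected benchmark would put two thresholds in one table, and a subject at 3 before belimumab would rebound at 4. The SAP was written with enrolment complete, in an open-label study, which is a poor time to replace a protocol-defined endpoint. This stands too, and it is why the change below is an addition.

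A reader might expect many false rebounds as well. A model that builds the off-drug score on the pre-belimumab score plus 0 to 4 points, with no mean fall on placebo, calls 23-32% of subjects who are not above that level rebounds. It ignores that holiday subjects must enter at 3 or below. Starting from an assumed 0 to 3 with the same noise and a rise of 2 to 4 points, false calls fall to about 1-3%, while the missed share stays large. Long-term discontinuation subjects may enter at any score, so this anchoring does not apply to them.

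Finally, time to flare, severe flare, flare rate and PGA use Day 0 of this study and are untouched, and individual SELENA SLEDAI results are listed. This limits the damage, but none of these displays shows rebound against the pre-belimumab level.

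**Conclusion.** The point holds in a limited form. For parent-placebo subjects, Table 2.6 does not compare off-drug activity with activity when belimumab was started, and no planned display does so or splits rebound by parent arm. Their status can be misclassified relative to that level; it is not misclassified in every case, since a score above both benchmarks, or above neither, is read the same way under both rules.

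Undercounting is the more plausible direction, because selection on a high entry score makes a later fall likely. That is inference. A reader might go further and conclude that the gap is about a year for everyone, or that stopping will look safer than it is. The documents support the year for BEL113750 only. They report neither the parent-placebo share nor any score change on placebo, and the flare endpoints give separate evidence on stopping. The percentages above are illustrations and not estimates for this trial. The right label is a cheap improvement.

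**What to change.** - Keep rebound against parent Day 0 as the main Table 2.6.
- In SAP Sections 7.2.1.3 and 7.2.3 and in the display list, add a sensitivity version of Table 2.6. For parent-placebo subjects it uses the last SELENA SLEDAI score before the first belimumab dose; for parent-belimumab subjects it keeps parent Day 0.
- Report the number of subjects, and rebound, by parent-study arm within each group.
- Footnote the other displays that use the parent baseline (SELENA SLEDAI change and the biomarker displays) to say that for parent-placebo subjects the change includes the placebo period.

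The cost is one extra table, parent-arm counts, footnotes, and one more score per parent-placebo subject. That score should sit in parent or feeder data already being drawn on, though SAP Section 5.3.1 warns that the BEL114333 data were not fully cleaned. No new subjects or visits are needed. The drawback is a low threshold for subjects with little activity before belimumab, so small rises will count for them. That is why this is a sensitivity display and not a replacement.

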5.3.2. Derivations and Handling of Missing Baseline Data

NOTES:

 Unless otherwise specified, the baseline definitions specified in Section 5.3.1 Baseline Definitions will be used for derivations for endpoints / parameters and indicated on summaries and listings.

 Unless otherwise stated, if baseline data is missing no derivation will be performed and baseline will be set to missing.

5.4. Multicentre Studies

In this multicentre global study, enrolment will be presented by investigative site, and in selected displays by country and investigative site.

Since this is a non-randomized study, results will be descriptive only, and there will be no methods applied to address multiple centers.

5.5. Other Considerations for Data Analyses and Data Handling Conventions

Other considerations for data analyses and data handling conventions are outlined in the appendices:

Section	Component	
13.1	Appendix 1: Protocol Deviation Management and Definitions for Per Protocol Population	
13.2	Appendix 2: Schedule of Activities	
13.3	Appendix 3: Assessment Windows	
13.4	Appendix 4: Study Phases and Treatment Emergent Adverse Events	
13.5	Appendix 5: Data Display Standards & Handling Conventions	
13.6	Appendix 6: Derived and Transformed Data	
13.7	Appendix 7: Reporting Standards for Missing Data	
13.8	Appendix 8: Values of Potential Clinical Importance	
13.9	Appendix 9: Adverse Events of Special Interest	
13.11	Appendix 10: Abbreviations & Trade Marks	
13.12	Appendix 11: List of Data Displays	
13.12	Appendix 12: Example Mock Shells for Data Displays	

6. STUDY POPULATION ANALYSES

6.1. Overview of Planned Demography, Baseline Characteristics and Medical History Analyses

The study population analyses including analyses of subject's disposition, protocol deviations, demographic and baseline characteristics, medical conditions, prior and concomitant medications, and exposure and treatment compliance will be based on the ITT population, or for the Screened population where specified. Data will be presented by treatment group and for all subjects combined, unless otherwise specified.

Full details of data displays being presented in Appendix 11: List of Data Displays.

Completion and withdrawal status by treatment phase is defined in Section 13.6.2.

6.2. Baseline Disease Activity and Other Baseline Endpoints

A summary of baseline disease activity will be provided, including counts and percentages for categorical endpoints and descriptive statistics for the continuous endpoints and scores.

Table 3 provides indicators of baseline disease activity that will be summarized. Some of these parameters will be summarized on the by visit summary for that parameter according to the table specifications.

Endpoint	Categories & Summaries at Baseline
SELENA-SLEDAI category	Continuous
	Categorical
	• 0, 1, 2, 3
SELENA SLEDAI by organ domain	Categorical
and item at baseline	Presented if Yes
Complement & BLyS Levels	Complement C3 and C4 (mg/dL)
	Continuous
	Categorical
	Positive, Negative
	Low, Normal, High
	(See Section 13.6.6 for definitions)
	BLyS Protein [ng/mL]
	Continuous
	Categorical
	 Below LLOQ: <0.061 ng/mL for China samples and <0.02048 ng/mL for all others
SLE Flare Index	Categorical
	At least 1 flare, At least 1 severe flare
PGA	Continuous
	Categorical
	• 0-1, >1 – 2.5, > 2.5
SLICC/ACR Damage Index	Continuous
	Categorical
	• 0, 1, > 1

Table 3 Baseline Disease Activity Endpoints

2018N381035_00 BEL116027

Endpoint	Categories & Summaries at Baseline
Proteinuria (based on spot urine using protein: creatinine mg/mg ratio)	Continuous Categorical (units are g/24hr equivalent) • $\leq 0.5, > 0.5$ • Subcategories of > 0.5 • $>0.5 - < 1$ • $1 - < 2$ • ≥ 2
B cells: CD19+ CD20+ CD20+/27+ memory CD20+/27- naïve CD20+/69+ activated CD20+/138+ plasmacytoid CD19+/27 ^{BRIGHT} /38 ^{BRIGHT} SLE subset CD20-/138+ plasma	Continuous
Autoantibody Levels	Anti-dsDNA [IU/mL] Continuous Categorical Positive: >=30 IU/mL Negative: <30 IU/mL ANA [Titer] Continuous Categorical Positive: Index >=0.80 Negative: Index <0.80 aCL Status Categorical Positive, Negative, Missing (See Section 13.6.6 for definitions)
anti-dsDNA and/or ANA positive	Categorical • Yes, No
Immunoglobulin Levels (IgG, IgA, and IgM [g/L])	Continuous Categorical IgG • Low: < 6.94 g/L, High: > 16.18 g/L IgM Low: < 0.48 g/L, High: > 2.71 g/L IgA • Low: < 0.81 g/L, High: > 4.63 g/L

Endpoint	Categories & Summaries at Baseline		
Allowable SLE Medication Usage	 Categorical: Steroid Only Immunosuppressant Only Anti-malarial Only Steroid and Immunosuppressant Only Steroid and Anti-Malarial Only Immunosuppressant and Anti-Malarial Only Isteroid and Immunosuppressant and Anti-malarial Traditional Chinese Medicine - Glycosides of Paeony/Tripterygium 		
Average daily prednisone dose (mg/day) at baseline	Continuous Categorical • $0, >0$ to $\leq 7.5, >7.5$		
PT/aPTT	Continuous		

6.3. Study Population Data for Maintenance Phase Subject Profile

Basic demography information will be listed on the subject profile.

7. EFFICACY ANALYSES

For all efficacy analyses, results for the TH group will be presented for the treatment holiday (TH) and re-start (RS) phases separately.

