4.3. Exclusion Criteria

Deviations from exclusion criteria are not allowed because they can potentially jeopardize the scientific integrity of the study, regulatory acceptability or subject safety. Therefore, adherence to the criteria as specified in the protocol is essential.

Subjects meeting any of the following criteria must not be enrolled in any of the 3 subject groups in the study:

- 1. Undue risk: Have developed clinical evidence of significant, unstable or uncontrolled, acute or chronic diseases not due to SLE (i.e., cardiovascular, pulmonary, hematologic, gastrointestinal, hepatic, renal, neurological, malignancy or infectious diseases), or experienced an adverse event (AE) in the belimumab continuation studies BEL114333, HGS1006-C1066, or LBSL99 studies that could, in the opinion of the principal investigator, put the subject at undue risk.
- 2. **Subject suitability:** Have developed any other medical diseases (e.g., cardiopulmonary), laboratory abnormalities, or conditions (e.g., poor venous access) that, in the opinion of the principal investigator, makes the subject unsuitable for the study.

Subjects meeting any of the following additional criteria must not be enrolled in the **control or treatment holiday groups** in the study:

- 1. **SLE:** New mild-moderate or severe flare as defined by the SLE Flare Index during the 30 day screening period prior to Day 0.
- 2. **Steroids:** Prednisone (or prednisone equivalent) greater than 20mg/day within the 30 day screening period.
- 3. New agents: Any new immunosuppressive/immunomodulatory agent, anti-malarial, or NSAID within the 30 day screening period prior to Day 0. However, any NSAID use for < 1 week is allowed.

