2.2. Study Objective(s) and Endpoint(s)

Objectives	Endpoints
Primary Objectives	Primary Endpoints
 Characterize the efficacy of a 24-week withdrawal followed a 28-week reintroduction of intravenous belimumab thera compared with uninterrupted intravenous belimumab thera for 52 weeks in subjects with SLE disease activity receivin belimumab 10 mg/kg plus standard of care, as measure by time to first flare. 	by ipy low g
Secondary Objectives	Secondary Endpoints
• Evaluate the rate of any flare	 Rate of any SLE Flare Index flare per subject year. Time to first SLE Flare Index severe flare.
 Assess safety. 	 Adverse events AESI Laboratory parameters Vital signs
Assess SLE disease activity.	 Number of subjects in the treatment holiday and long-term discontinuation group with evidence of rebound (defined as a SELENA SLEDAI score during the first 24 weeks that exceeds the baseline SELENA SLEDAI score in the subjects' respective original parent study). SELENA SLEDAI scores change from baseline.
Assess immunogenicity.	Response (Negative, Transient Positive, Persistent Positive) by Visit and Across All Visits
 Assess markers of autoimmuresponse (e.g., immunoglobulins, compleme 	anti-dsDNA, ANA, C3, and C4.

Objectives	Endpoints	
	(CD19+, CD20+, CD20+/27+ memory, CD20+/27– naïve, CD20+/69+ activated, CD20+/138+ plasmacytoid, CD19+/27BRIGHT/38BRIGHT SLE subset and CD20-/138+ plasma cells) at Weeks 0, 8, 16, 24, 32, 40 and 52 and from Weeks 24 to 52.	
 Assess changes in corticosteroid use. 	 Number of days of daily prednisone dose ≥7.5 mg/day and/or increased by 25% from Day 0 of this study to Week 24, from Day 0 of this study to Week 52, and from Week 24 to Week 52. 	
	 Number of days of daily prednisone dose ≤7.5 mg/day and/or decreased by 25% from Day 0 of this study to Week 24, from Day 0 of this study to Week 52, and from Week 24 to Week 52. 	
Exploratory/Other	Exploratory/Other Endpoints	
	Time to first renal flare	
	 Time to first renal flare among subjects with baseline proteinuria >0.5g/24hr equivalent 	
	Change from Baseline in PGA	
	 Change and percentage change from Baseline in BLyS Protein 	
	SLICC/SDI	
	Change from Baseline	

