7.2. Secondary Efficacy Analyses

7.2.1. Endpoint / Variables

7.2.1.1. Rate of Flares

The unadjusted rate of flares per subject-year over 52 weeks will be summarized by treatment group.

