13.4.1.1. Treatment Holiday Group

Endpoint	Day 0 Visit Parent Study	Day 0 Visit BEL116027 Study	Week 24/ TX Re-start Visit	Week 52/ Exit/Escape Visit	Week 16 Follow- up Visit	
		Baseline				
Flare, PGA, Prednisone,	N1/A	52-Week Trea	atment Phase	Maintenance		
SLICC	N/A	Holiday Phase	Re-start Phase	Phase	N/A	
	I	Baseline			1	
SS, Auto-antibodies	Pre-Study	52-Week Trea	atment Phase	Maintenance	N1/A	
Immunoglobulins, B-cells [1], BLyS	Phase	Holiday Phase	Re-start Phase	Phase	N/A	
		Baseline	1		1	
Rebound [2]	Pre-Study	52-Week Trea	atment Phase			
	Phase	Holiday Phase	N/A	N/A	N/A	
	L	Baseline			1	
Adverse Events, Lab		52-Week Trea	atment Phase	Maintenance		
Parameters, Vital Signs, Con Meds Immunogenicity [1]	N/A	Holiday Phase	Re-start Phase	Phase	N/A	

N/A = Not Applicable.

[1] Immunogenicity and B-cells may also be collected at the 6-month follow-up visit. The 6-month follow-up visit is not represented in the diagram since it does not define a treatment phase of the study.

[2] Rebound is only assessed up to the Week 24/Treatment re-start visit.

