13.4.1.2. Treatment Control Group

Endpoint	Day 0 Visit Parent Study	Day 0 Visit BEL116027 Study [1]	Week 24 Visit	Week 52/ Exit Visit	Week 16 Follow -up Visit				
		Baseline							
Flare, PGA, Prednisone, SLICC	N/A	52-Week Trea	atment Phase	Maintenance Phase	N/A				
Baseline									
SS, Auto-antibodies Immunoglobulins, B-cells [2], BLyS	Pre-Study Phase	52-Week Trea	atment Phase	Maintenance Phase	N/A				
		Baseline		•					
Rebound [3]		52-Week Trea	atment Phase						
	Pre-Study Phase	First 24 Weeks	N/A	N/A	N/A				
		Baseline		•					
Adverse Events, Lab Parameters, Vital Signs, Con Meds, Immunogenicity [2]	N/A	52-Week Trea	atment Phase	Maintenance Phase	N/A				

N/A = Not Applicable.

[1] If the first infusion date differs from the Day 0 visit date, then the first infusion date will be used as the phase cut-point.

[2] Immunogenicity and B-cells may also be collected at the 6-month follow-up visit. The 6-month follow-up visit is not represented in the diagram since it does not define a treatment phase of the study.

[3] Rebound is only assessed up to the Week 24 visit.

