- A reproducible decrease in GFR of >20%, accompanied by proteinuria (>1), and/or cellular (RBC and WBC) casts.
- [Alarcón-Segovia, 2003].

GFR is estimated by the Cockcroft-Gault equation [Cockcroft, 1976] for creatinine clearance in mL/min.

Cockcroft-Gault Equation

$$Cl_{cr} (mL/min) = \frac{(140\text{-}age (yrs)) \text{ x weight (kg)}}{72 \text{ x serum creatinine (mg/dL)}} \text{ x } 0.85 \text{ if female}$$

"Reproducible" requires the criterion to be met at two consecutive visits, including unscheduled visits.

The following table identifies the lab parameters to be used to evaluate the criteria in the renal flare definition above.

Criterion	Parameter	SI Dataset LBTESTCD
Proteinuria	Urine Protein:Creatinine Ratio (mg/mg)	PRTCRT_URQ
GFR	Creatinine Clearance estimated by the Cockcroft-Gault equation (mL/min)	CRTCE_PLR
Cellular casts:		
WBC cellular casts	WBC cellular casts	WBCSTM_URQ
dysmorphic RBCs	dysmorphic RBCs	DRBCM_URQ

SLE Flares and Severe Flares, and Renal Flares

Derivation for rates of SFI flares

• Within a treatment group, the unadjusted flare (severe flare) rate per subject-year in a given phase will be calculated as:

Unadjusted flare (severe flare) rate per subject-year =

total number of flares (severe flares) in the phase / total number of years of follow-up time in the phase.

• The calculation will not include baseline flares in the 116027 study.

Follow-up time derivation for rates of SFI flares		
Phase	Treatment Group	Definition
52-week Treatment Phase	TC, LTD	(Week 52/Exit visit date – Day 0 date + 1)/ 365.25 .
TH Phase	TH	(Week 24/TX re-start date – Day 0 date + 1)/ 365.25 .
RS Phase	TH	(Week 52/Exit visit – Week 24/TX re-start date)/ 365.25.

SELENA SLEDAI Organ System Domains

SELENA SLEDAI assessments consist of 24 individual weighted items in which signs and symptoms, laboratory tests, and physician's assessment for each of 8 organ systems are given a weighted score and summed if present (marked 'Yes') at the time of the visit or in the preceding 10 days. The maximum theoretical score is 105 (all 24 descriptors present simultaneously) with 0 indicating inactive disease (marked 'No'), but in practice few subjects have scores > 45 [Buyon, 2005; Petri, 2005].

Organ system domain scores are the sum of the weights of items within the organ domain as defined in the table below.

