13.11.5. Efficacy Tables

Efficacy	: Tables			
No.	Population	Title	Programming Notes	Priority Headline Results denoted by H
Flares				
2.1.	ITT	Time to First SFI Flare to Week 52	Primary endpoint	Н
2.2.	ITT	SFI Flares per Subject-year from Day 0 to Week 52	Secondary endpoint	
2.3.	ITT	Time to First SFI Severe Flare to Week 52	Secondary endpoint	Н
2.4.	ITT	Time to First Renal Flare to Week 52	Exploratory endpoint	Н
2.5.	ITT	Time to First Renal Flare to Week 52 [1] Among Subjects with Baseline Proteinuria >0.5g/24hr Equivalent	Exploratory endpoint	
Reboun	d and SELENA-	SLEDAI		
2.6.	ITT	SELENA SLEDAI Rebound (LOCF) (52-Week Treatment Phase)	Secondary endpoint	Н
2.7.	ITT	SELENA SLEDAI Change from Baseline (LOCF) (52-Week Treatment Phase)	Secondary endpoint	
PGA		·		
2.8.	ITT	PGA Change from Baseline (52-Week Treatment Phase)	Other/exploratory endpoint	
Prednis	one			
2.9.	ITT	Number of Days of Daily Prednisone Dose >=7.5 mg/day and/or Increased by 25%	Secondary endpoint	
2.10.	ITT	Number of Days of Daily Prednisone Dose <=7.5 mg/day and/or Decreased by 25%	Secondary endpoint	

Efficacy	Efficacy: Tables				
No.	Population	Title	Programming Notes	Priority Headline Results denoted by H	
2.11.	ITT	Prednisone Percent Change from Baseline (52-Week Treatment Phase)	Other/exploratory endpoint		
2.12.	ITT	Prednisone Reduced to <= 7.5 mg/day by Visit (DO/TF=NR) among Subjects with Baseline Prednisone Dose > 7.5 mg/day (52-Week Treatment Phase)	Other/exploratory endpoint		

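### Secondary flare rate: the SAP promises a Day 0 to Week 52 rate by group, but its derivation gives the holiday group only phase rates and the controls only an undivided 52-week rate

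*SAP*

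**What the plan says.** SAP 7.2.1.1 defines the secondary endpoint this way: "The unadjusted rate of flares per subject-year over 52 weeks will be summarized by treatment group". The title of Table 2.2 in 13.11.5 agrees: "SFI Flares per Subject-year from Day 0 to Week 52". SAP 7.2.2.1 asks for flares, subject-years and the rate in a time interval that it does not name.

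The opening of SAP Section 7 sets a rule for all efficacy analyses: "results for the TH group will be presented for the treatment holiday (TH) and re-start (RS) phases separately".

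SAP 13.6.3 computes the rate within a given phase, as "total number of flares (severe flares) in the phase / total number of years of follow-up time in the phase". Its follow-up table has three rows:

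- 52-week treatment phase, for TC and long-term discontinuation (LTD) only: Week 52/Exit minus Day 0, plus 1, over 365.25.
- Holiday phase, for TH only: Week 24/re-start minus Day 0, plus 1, over 365.25.
- Re-start phase, for TH only: Week 52/Exit minus Week 24/re-start, over 365.25.

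SAP 13.4.1 applies the name 52-week treatment phase to all three groups. The TH diagram in 13.4.1.1 draws that phase across the holiday and re-start phases, ending at the "Week 52/ Exit/Escape Visit". In 13.4.1.2 the TC flare row is one undivided 52-week phase.

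**The concern.** Followed literally, the derivation puts two TH phase rates next to one 52-week TC rate, under a title that promises Day 0 to Week 52. The table would then show neither the 52-week contrast named in 7.2.1.1 nor a contrast over the same weeks.

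Dividing by subject-years removes the difference in window length. It does not remove a change in the control rate during the year. Some change is plausible, because Protocol 4.3 excludes TH and TC candidates with "New mild-moderate or severe flare as defined by the SLE Flare Index during the 30 day screening period prior to Day 0". Both groups therefore start from a selected quiet period.

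What is at stake is how a descriptive secondary endpoint is read. An apparent rise or fall during the holiday could reflect the calendar window and not the withdrawal of belimumab.

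**Working it through.** The plan states no flare rate per subject-year, so there is no figure of its own to reproduce. The pooled BLISS figures in SAP Section 2 are percentages of subjects with a flare. They are not event rates before and after Week 24.

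**Inputs.** Week 24 is 168 days and Week 52 is 364 days after Day 0 (Protocol Table 2). These match target study days 169 and 365 in SAP 13.3.3, where Day 0 is Study Day 1. Enrolment is 12 TH and 29 TC (SAP 2.3). The formulas are those of 13.6.3. Complete follow-up at nominal visit days is assumed.

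**Step 1: do the TH rows add up to 52 weeks?**

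- Holiday phase: 168 − 0 + 1 = 169 days.
- Re-start phase: 364 − 168 = 196 days.
- Sum: 365 days, the same as the TC row (364 − 0 + 1 = 365).

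The 52-week TH rate is therefore (holiday flares + re-start flares) / (holiday years + re-start years).

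**Step 2: subject-years, n × days / 365.25.**

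| Group | Day 0 to Week 24 | Week 24 to 52 | Day 0 to Week 52 |
|---|---|---|---|
| TH, n = 12 | 5.55 | 6.44 | 11.99 (not specified) |
| TC, n = 29 | 13.42 (not specified) | 15.56 (not specified) | 28.98 |

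**Step 3: effect of unmatched windows.** Let the control rate be λ up to Week 24 and rλ after it. The value of r is not in the documents, and 0.5 to 2 is an assumed range. Suppose TH has exactly the control rates, so there is no true difference.

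- Undivided control rate: λ(169 + 196r)/365.
- Holiday-phase rate over undivided control rate: 365/(169 + 196r).
- Re-start-phase rate over undivided control rate: 365r/(169 + 196r).

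| r | Holiday / TC | Re-start / TC |
|---|---|---|
| 0.5 | 365/267 = 1.37 | 182.5/267 = 0.68 |
| 1 | 365/365 = 1.00 | 365/365 = 1.00 |
| 1.5 | 365/463 = 0.79 | 547.5/463 = 1.18 |
| 2 | 365/561 = 0.65 | 730/561 = 1.30 |

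**Step 4: the matched comparisons.** With the same assumptions, the 52-week TH rate over the 52-week TC rate is 1.00 for every r. So is each TH phase rate over the TC rate for the same weeks. The distortion comes only from the window mismatch.

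**The case against.** The strongest reply is that nothing is lost. The two TH rows partition the year exactly, the 52-week phase already exists for TH in 13.4.1, and the missing label looks editorial. That stands for the 52-week TH rate: it is unspecified but recoverable. It does not supply the other half, because no Week 24 split of TC flares and follow-up is written anywhere.

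A second reply is that the table shells (SAP 13.12) are available only on request and may already show a TH total or a split TC column. This also stands as a limit: the final layout cannot be seen. The shells would still have to depart from, or add to, the 13.6.3 derivation.

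A third is that the size of the distortion rests on an assumed r and vanishes at r = 1, and that with 12 TH subjects chance variation in the phase rates will be large anyway. Both points are correct.

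Precedent for matched windows elsewhere in the SAP is helpful but modest. The prednisone-day endpoints in 2.2 run from Day 0 to Week 24, "from Day 0 of this study to Week 52, and from Week 24 to Week 52", although that text names no group. In 13.4.1.2 the note for TC is "Rebound is only assessed up to the Week 24 visit", but that window belongs to the definition of rebound. Prednisone sits in the same undivided TC row as flare, so that row alone does not rule out a split.

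Figure 2.1 and the SFI flare listing (Listing 43) would give some view of timing in the controls. The figure covers first flares only, and the listing is not a summary.

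**Conclusion.** The point holds as a specification gap in one secondary, descriptive endpoint. The plan promises a Day 0 to Week 52 rate by group and does not define it for TH. It defines TH rates by phase with no TC rate over the same weeks. The text is clear on both counts. The effect on the displayed ratio is not known from the documents: none if the control rate is constant, and 1.37 to 0.65 for the holiday phase over the assumed r of 0.5 to 2, with equal true rates and complete follow-up. Neither the direction nor the presence of a distortion can be asserted in advance. SAP 2.4 rules out inference, so no error rate or power is affected.

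A reader might infer that the 52-week comparison is impossible. It is not, because the phases sum to 365 days. A reader might also infer from the Section 7 rule that the primary endpoint has the same fault. The documents do not support that: SAP 7.1.1, 7.1.2, 7.1.5 and 13.7.2.1 all describe one time-to-first-flare estimate from Day 0 to Week 52, so the primary analysis is outside this point.

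**What to change.** 1. In the 13.6.3 follow-up table, add TH to the 52-week row, with TH time ending at the Week 52/Exit/Escape visit as 13.4.1.1 already draws it. Report that rate in Table 2.2 in addition to the two phase rates.
2. Wherever TH flare rates are shown by phase, show TC for Day 0 to Week 24 and for Week 24 to Week 52, using the same two formulas and the existing rule in 13.4.1 for events on a cut-point date.

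The cost is one amended row label with its end point, a sentence or two in the SAP, and extra TC columns in Table 2.2. The visit dates and flares are already collected, and no study procedure changes.
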